#### 5.5.2 Risks and Benefits of the Optional EMA Protocol

Reasonably foreseeable physical, psychological, social, economic and privacy risks, side effects or discomforts associated with the research and their expected frequency and severity:

Loss of confidentiality:

- The primary risk is the potential for loss of confidentiality. This risk is not expected to be greater than the risk of loss of confidentiality routinely involved in accessing mental health care via a virtual platform. In order to mitigate privacy risks that are inherent to using mobile phones and websites, we will be implementing several strategies.
- First, all information collected outside of the VA network will be gathered via Qualtrics surveys that are protected using SSL certification to ensure the encryption of all information shared between the study website and potential participants. Accordingly, all responses related to the screening questions, consent process, and survey instruments will be encrypted prior to being uploaded to the study server. We will be using the VA Office of Research Development (ORD)'s instance of the Qualtrics application, which resides in the FedRAMP environment. This has been approved under the Authorized to Operate (ATO) to store "moderate level protected health information and personally identifiable information". This level of security is maintained even when participants complete study surveys on personal devices, such as their own mobile devices.
- Study records will be maintained in a secure location (at Minneapolis, this is the R: drive) and destroyed according to VA Federal Records requirements in VHA Record Control Schedule (RCS 10-1), currently at 5 fiscal years following the closure of the study.
- The following personal identifiers are necessary to deliver surveys on Qualtrics: name, email address, and phone number. All of these identifiers will be tracked in central Participant Spreadsheet that tracks participants in our study, stored on the R: drive. Once enrolled, text and/or email will be used to send reminders to complete study surveys, schedule interviews, and answer any questions that participants may have as they are completing the EMA protocol, unless the participant requests we contact them by phone call instead. Names and telephone numbers must be inputted into Qualtrics to send EMA surveys via text message.
- All personal identifiers will be permanently removed from the dataset at the conclusion of the study, ensuring that the final dataset for analysis is fully de-identified. To enable merging our dataset with the data at JJP VAMC, we will establish ID numbers with the JJP VAMC team prior to deleting any identifying information.
- In addition to the above measures, we will ensure staff are trained in protections for PII and PHI prior to accessing any study data.

#### Burden of protocol:

- Veterans may perceive the protocol to be burdensome and may become frustrated with the frequency or repetition of the daily assessments. Based on past research, we expect this frustration to be low in intensity, as most frustrated participants simply choose not to respond to the survey, which alleviates the frustration. Also, the intensity of the proposed protocol (one 3-minute survey per day for one week at a time; three bursts) is considerably lower than the average ecological momentary assessment study (4 surveys per day for 4 continuous weeks; Jones et al., 2019). The risk of excess burden will be further minimized by reducing the length of surveys to the minimum necessary, designing surveys to accommodate skipped questions, encouraging Veterans to end the assessment as soon as they sense fatigue, and making the daily assessment portion of the original study optional. If a Veteran expresses frustration with the protocol, we will offer to terminate their participation in the daily assessment protocol with no impact on their enrollment in the clinical trial taking place at JJP VAMC. Finally, we will adjust the protocol's length and/or intensity if Veterans report that either of these is unacceptable.

#### Discomfort with questions:

- The daily assessments will ask Veterans to reflect on and report their current mental health and long COVID symptoms, including levels of hopelessness, loneliness, and ability to function. This process may increase Veterans' awareness or focus on their own symptoms or impairment. Though increased awareness is often desirable in treatment and can result in improvements in mental health outcomes, it is possible that increased awareness may increase distress as well. Veterans will be provided with resources (i.e., Clinic contact info, principal investigator info, and the Veterans Crisis Line) at the end of every survey in the event that they need support. They will be encouraged to reach out to the principal

investigator to withdraw from the study if the surveys are upsetting (with no impact to the care they receive at their VA or in the main clinical trial), and JJP VAMC mental health providers (primarily the co-investigators on the JJP VAMC clinical trial, who are clinicians for the proposed participants) will be in contact with the principal investigators at both sites if a Veteran shares that the study is upsetting.

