## 5.2 Recruitment Methods

Long-COVID Patients will be recruited through recruitment from James J. Peters VAMC Long-COVID clinical program and clinician referrals. The Bronx had significantly higher rates of COVID-19 infection than other boroughs in New York City. Thus, recruitment of *up to 36 Veterans* is feasible within the 18-month timeframe.

**Limitations and Future Directions.** One potential issue may be the recruitment of Veterans with Long-COVID. However, a strength of the proposed study is it's involving telehealth, making it more appealing to participants and less prone to no-shows. We will also recruit from our in-house Long-COVID center and multiple existing national Long-COVID programs. While the JJPVAMC is diverse in race and ethnicity, our

study may still have a diversity limitation as it will be conducted in an urban northeast VAMC and may not fully generalize to other areas of the USA. Future studies should extend the findings across other VAMCs. During year 2 we will submit a Merit Award to complete the planned follow up study testing the final manualized version of LC-CR (developed in this SPiRE project) in a multi-site clinical efficacy RCT.

Veteran participants will be offered financial compensation for their participation based on completion levels of the following:

Research Procedure for LC-CR	Participant Compensation
Pre-Treatment Baseline Assessment	\$75
Post-Intervention Assessment (Mod 1)	\$75
Post-Intervention Assessment (Mod 2)	\$75
Post-Intervention Qualitative Interview (Mod 2).	\$75

You will also receive a \$50 bonus upon completion of each therapy module (after the first 8 sessions and after the second 8 sessions).

Participants who consent to enroll in the EMA portion of the research study will be compensated for their participation. The JJPVAMC will be responsible for compensating patients. Participants will be compensated per survey initiated (i.e., at least one question is answered). Participants can receive up to \$135 across all three week-long bursts of daily surveys.

At this time, we anticipate providing a maximum of \$135 per person for participating. Each burst listed below lasts for 7 days. The payment schedule is as follows:

- Burst 1, baseline: \$4 per daily assessment initiated
  - Maximum: \$28 for this burst
- Burst 2, mid-treatment: \$5 per daily assessment initiated
  - Maximum: \$35 for this burst
- Burst 3, end of treatment: \$6 per daily assessment initiated
  - Maximum: \$42 for this burst

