- In addition, we will offer an extra \$10 incentive for initiating 5 or more daily assessments per burst.
- Thus, total possible is \$135 per person, including all \$10 bonuses.

Note: initiation means filling in at least 1 question on the survey (out of approximately 20).

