We ensure that the information being communicated to the participant during the consent process will not include exculpatory language through which the investigator, the sponsor, the institution, or its agents are released from liability by providing patients with contact information for the PIs and co-investigators should they feel that they have suffered an injury. Furthermore, patients are informed in the consent document that if they are eligible veterans, they are entitled to medical care and treatment if they experience any adverse effects resulting from the study. Participants are also provided with the contact information for the JJP VA IRB should they have questions regarding the research or their rights.

The informed consent form includes information related to the procedures, risks, and benefits of the optional EMA study. Those participants who consent to the optional EMA study will be given an Information Sheet with additional information about the EMA study, its risks and benefits, and assessment and compensation plan.

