## **5.4 Inclusion/Exclusion Criteria**

Inclusion criteria include: (1) U.S. Veteran (2) Age 18-80 (3) Screened positive for Long-COVID (e.g., COVID-19 positive, diagnosed with a PCR test and/or an antibodies blood test, and symptoms lasting 1 month or longer after infection (4) Participation in VA Services the JJPVA (5) Sufficient clinical stability and readiness to participate in a group therapy as deemed by their VA Service provider,

Exclusion criteria include: (1) Active alcohol or opiate dependence requiring medically supervised withdrawal. (2) Active psychosis. (3) MINI Mental Status < 23 or inability to function in a group setting. (4) Those unable to operate telehealth platforms or other devices. (5) Unable to speak English. (6) Lack of capacity to consent. (7) Unable or unwilling to provide at least one contact for emergency purposes.

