Participants who consent to enroll in the EMA portion of the study may find may perceive the protocol to be burdensome and may become frustrated with the frequency or repetition of the daily assessments. Based on past research, we expect this frustration to be low in intensity, as most frustrated participants simply choose not to respond to the survey, which alleviates the frustration. Also, the intensity of the proposed protocol (one 3-minute survey per day for one week at a time; three bursts) is considerably lower than the average ecological momentary assessment study (4 surveys per day for 4 continuous weeks; Jones et al., 2019). The risk of excess burden will be further minimized by reducing the length of surveys to the minimum necessary, designing surveys to accommodate skipped questions, encouraging Veterans to end the assessment as soon

as they sense fatigue, and making the daily assessment portion of the original study optional. If a Veteran expresses frustration with the protocol, we will offer to terminate their participation in the daily assessment protocol with no impact on their enrollment in the clinical trial taking place at JJP VAMC. Finally, we will adjust the protocol's length and/or intensity if Veterans report that either of these is unacceptable.

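### Minor: the EMA support contacts, including the Veterans Crisis Line, are placed only at the end of each daily survey, so a Veteran who stops partway may not see them that day

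*Protocol*

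**What the plan says.** Protocol 5.5.1 describes an optional EMA component of three week-long bursts of daily surveys, at baseline, mid-treatment and end of treatment. Each survey has about 20 questions, takes about 3 minutes and is sent at the end of the day.

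Section 5.5.2 (Discomfort with questions) says that items on hopelessness, loneliness and functioning may raise distress. Its response at the survey itself is: "Veterans will be provided with resources (i.e., Clinic contact info, principal investigator info, and the Veterans Crisis Line) at the end of every survey". Section 7a repeats the sentence.

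Section 5.5.2 (Burden of protocol) limits burden by "designing surveys to accommodate skipped questions, encouraging Veterans to end the assessment as soon as they sense fatigue". Section 7a again has "encouraging Veterans to end the assessment as soon", and the sentence continues after a page break.

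On payment, section 5.2 says: "Participants will be compensated per survey initiated (i.e., at least one question is answered". It adds that "initiation means filling in at least 1 question on the survey (out of approximately 20".

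**The concern.** The answer to burden and the answer to distress pull in different directions. One invites the Veteran to leave the survey early, and the other puts the support contacts where only those who reach the end are sure to see them. Payment gives no reason to continue to the last screen. Early stopping is foreseeable, because the Abstract and section 2.0 list prolonged fatigue first among common Long-COVID symptoms and the stop cue is fatigue.

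What is at stake is whether the Veteran sees the list early and reliably, above all the Veterans Crisis Line. The surveys arrive at the end of the day, and the protocol does not describe anyone reading the answers as they come in.

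**Working it through.** The point is mainly one of reading, and the plan gives no figure to reproduce.

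**Step 1: the two instructions side by side.** The contacts come at the end of every survey (5.5.2 and 7a, Discomfort). Veterans are encouraged to end on fatigue (5.5.2 and 7a, Burden). No section mentions a copy of the contacts on the first screen. No section says what a Veteran sees after leaving early. Followed literally, someone who stops partway may not see the list that day.

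**Step 2: where else the contacts appear.** Section 5.3 says that consent gives contact details for the investigators, framed around injury, and for the IRB. The Crisis Line is named only in the end-of-survey sentence and its repeat. Section 5.3 also says that EMA participants "will be given an Information Sheet with additional information about the EMA study, its risks and benefits". That sheet and the consent pages are not in the file and may carry the full list.

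**Step 3: how much could be missed.** The documents give no early-stop rate. Let p be the share of opened surveys ended before the last screen. It is an assumption, taken as constant and independent across days, with no contacts shown on early exit.

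- Surveys per Veteran: 3 bursts x 7 days = 21 at most.
- Chance that the first opened survey does not show the list: p.
- Expected opened surveys until the list is first seen: 1/(1-p).
- Chance that it is not seen in burst 1, with all 7 surveys opened: p^7.

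| Assumed p | First survey misses the list | Expected surveys to first sight | Never seen in burst 1 |
|---|---|---|---|
| 5% | 5% | 1/0.95 = 1.05 | 0.05^7 = 7.8e-10 |
| 25% | 25% | 1/0.75 = 1.33 | 0.25^7 = 0.006% |
| 50% | 50% | 1/0.50 = 2.0 | 0.5^7 = 0.8% |
| 90% | 90% | 1/0.10 = 10 | 0.9^7 = 48% |

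The 90% row stands in for a habitual early stopper. Nothing in the documents supports that value. It is shown because stopping tends to cluster within a person, which the independence assumption ignores. The figures count stops for any reason, not stops by distressed Veterans, who are the group that matters.

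**Step 4: first-screen placement.** Everyone who opens a survey passes the first screen, so the list is shown at the first opened survey whatever p is.

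**The case against.** The strongest reply is that this is a layout preference in an optional sub-study and that the list is not the protocol's only answer to distress. Much of that stands.

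- The sentence right after the quoted one, in both 5.5.2 and 7a, encourages Veterans to contact the principal investigator to withdraw if the surveys upset them. It also has the treating clinicians contact the investigators at both sites when a Veteran reports this. Neither step is said to depend on finishing a survey, though both need the Veteran to speak up.
- Other safeguards apply: the SBQ-R at three time points (5.5), a safety plan for distress found at follow-up assessments (7a), chart review for a mental health provider and safety plan with clinicians available to evaluate (8.0), and outreach with the suicide prevention team on withdrawal (5.7). Section 5.4 also excludes anyone "Unable or unwilling to provide at least one contact for emergency purposes".
- Exit routing is undescribed, so leaving early might still bring up the resource page. Skipped questions are accommodated, so a tired Veteran may be able to click through to it.
- The stop cue is fatigue, whereas the list answers distress. The overlap between the two cannot be estimated from the documents.
- Crisis-line text shown before hopelessness items could affect the answers. That is a reason not to repeat it on every screen, and it counts to a lesser degree against a first screen too.

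These arguments lower the weight but do not close the gap: no section guarantees that a Veteran who closes a survey early is shown the Crisis Line.

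A reader might infer that EMA participants are left without crisis support, or that the safety plan fails. The documents do not support that, given the routes above and the unseen consent materials. A reader might also fault the payment rule. Paying on initiation puts no pressure on a Veteran to finish upsetting items and should stay.

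**Conclusion.** The point holds as a minor, optional improvement to participant protection. As written, a Veteran who stops partway may miss the contacts that day, and the Crisis Line is named nowhere else in the documents. The loss is mostly one of delay, because one survey completed or skipped through shows the list and later repeats add little. At assumed early-stop rates of 5% to 25%, first sight comes after 1.05 to 1.33 opened surveys on average. Only a habitual early stopper would go a whole burst without it. These figures are illustrative and rest on an assumed p, on independence across days and on an early exit that shows nothing.

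Eligibility, sample size and the planned analyses are unaffected; neither section 5.6 nor the SAP specifies an EMA analysis. The SAP reports its analyses in the past tense, so the bursts may already be over. In that case the change matters only if the surveys are reused, for instance in the planned RCT.

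**What to change.** In Protocol 5.5.2 (Discomfort with questions) and its repeat in 7a, change the placement to: *on a brief, neutral first screen and at the end of every survey*. Where the survey software allows, route an in-survey early exit to the same resource page. Keep the contacts, the right to stop and the payment rule as they are.

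Do not put the contacts in the text message carrying the link, because 5.5.2 names loss of confidentiality as the primary EMA risk and mobile phones as a privacy concern. Do not repeat them on every screen.

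The cost is one phrase in two places, one text block in Qualtrics and, if feasible, one exit route. No staff, visits or data are added. The downside is a little more text in a roughly 3-minute survey and a small possible priming effect on the hopelessness items, kept low by neutral wording and identical display in all three bursts. The change does not reach Veterans who never open a survey, and the protocol expects that "most frustrated participants simply choose not to respond to the survey, which alleviates the frustration".

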## 5.6 Data Analysis

All data will be de-identified before it is entered into a redcap database at the JJPVA over the intranet.

**5a. Statistical approach.** Descriptive statistics will be calculated, and outcome measures will be compared across the time points using repeated-measures mixed models. Data will be used to examine acceptability and feasibility, and iteratively improve the treatment. Then, we will apply for a RR&D VA Merit to determine efficacy of LC-CR in an RCT.

**5b. LC-CR Fidelity Measure.** Our research team (Drs. [name] and [name]) have experience establishing fidelity of psychosocial interventions. After the first pilot, an adherence scale will be created to assess 1) general LC-CR requirements, 2) session specific requirements, and 3) general group psychotherapy requirements.

## 5.7 Withdrawal of Subjects

The recruitment process will not be coercive or unduly influencing, as participants enter the research study voluntarily and understand that they have the right to withdraw at any time. Subjects will be told that non-participation in the study will not affect any current treatments they are receiving at VA or elsewhere.

There are no consequences if subjects to withdraw from this study. For subjects that withdraw, our research team will work closely with the suicide prevention team to establish contact, assess reasons for discontinuing treatment and attempt to address concerns. This research team will ask for emergency contact numbers and an emergency contact person that may assist us if you drop from treatment or an emergency occurs.

## 6.0 Reporting

### 6a) Reporting in Medical Charts

Group sessions will be documented in the patients' CPRS charts. Each session will generate a progress note so that anyone reading the chart will be able to recognize that the patient is actively participating in the therapy and when the most recent group session was.

Adverse events will be monitored through regular contact with study participants, as well as contact with providers. Participants will be carefully monitored during the interview by the research staff who will be trained in noticing when the participant is uncomfortable or needs to take a break. Participants who demonstrated distress during the interview will be closely monitored through follow-up phone calls and the PI and RA will notify the primary provider of the participant's experience during the interview.

### 6b) Risk Management Plan:

To manage potential risk during group sessions, we will follow the OCC's **CAPS Lock process**; **C – Consent:** Obtain or confirm that verbal consent for telehealth has been documented. As part of this step, we will review the OCC approved Group Telehealth Agreement. This is a one-time requirement for service between a telehealth health care professional and a Veteran. **A – Address:** In the VVC e911 feature, obtain or confirm

the Veteran's present location and address. Pre-validate the address to validate whether e911 is available. Ensure that the location is private and safe. **P – Phone Numbers:** Obtain or confirm the Veteran's phone number. If others are present, obtain their name(s) and phone number(s). Obtain the name and phone number of the emergency contact if e911 is not available. We will also use the Emergency Call Relay Center [contact]) if e911 services are not available. **S – Survey:** Confirm that you can see and hear the Veteran. Identify all others in the room. Review with the Veteran and others present how to alert you if/when an emergency occurs. **Lock:** Lock the virtual medical room once all participants have joined.

In the event of an emergency during group sessions, we will follow the OCC's Emergency Handoff Procedures:

#### **Step 1 – Contact Emergency Services**

Use e911 services, the Emergency Call Relay Center at [contact], or contact the local emergency services or other emergency contact number that the Veteran provided. Give the dispatcher (or emergency contact number) the Veteran's location and specific information about the emergency.

#### **Step 2 – Remain in contact with the Veteran**

Remain in contact with the Veteran, either by VA Video Connect or by phone, until local emergency responders arrive.

#### **Step 3 – Hand off and document the incident**

Provide emergency responders (or the emergency contact) with the necessary information for a handoff. Complete the appropriate documentation following local facility procedures and Office of Connected Care guidance.

In addition, if a participant is in distress during the session, the co-therapist will be available to transfer off the group call to an individual call with that participant to evaluate, assess for safety concerns, and engage de-escalation strategies.

